3.8 User Interface

The PQ Bypass Stent Graft System currently requires one operator to deploy using standard percutaneous techniques. The PQ Bypass Stent Graft System does not interface and/or interact with other devices with the exception of standard ancillaries such as sheaths, guidewires, balloons, etc.

4.0 PROPOSED INTENDED USE

The PQ Bypass™ Stent Graft System is indicated to improve luminal diameter in the treatment of patients with symptomatic de novo or restenotic native lesions or occlusions of the superficial femoral artery (SFA) and/or proximal popliteal artery, with reference vessel diameters of 5.0 to 6.7 mm and lesion lengths up to 180 mm.

5.0 STUDY DESIGN

5.1 Study Design

Prospective, single arm, multi center, international, non randomized, pre market, safety and effectiveness clinical investigation.

5.2 Study Endpoints

Primary Safety Endpoint:

The primary safety endpoint for this study is freedom from a major adverse event (MAE) at 30 days post procedure. An MAE is defined as TLR, amputation of the treated limb, or death.

Primary Effectiveness Endpoint:

The primary effectiveness endpoint is defined as stent patency as evidenced by a peak systolic velocity ratio (PSVR) < 2.5 from DUS obtained within the 12 month visit window with no clinically driven re intervention within the stented segment.

Secondary Safety Endpoints:

Secondary safety endpoints will be evaluated and include:

1. The combined rate of death at 30 (± 7) days, target lesion revascularization (TLR), index limb amputation, and an increase in Rutherford Becker Classification by 2 classes (comparing pre to post procedural assessments) at 12 months.
2. Major adverse vascular event (MAVE) at 30 days, 6 months (180 ± 14 days) and 12 months (360 ± 30 days) defined as stent thrombosis, target limb amputation, clinically apparent distal embolization, defined as causing end organ damage (e.g. lower extremity ulceration, tissue necrosis, or gangrene), procedure related arterial rupture, acute limb ischemia, or bleeding event requiring transfusion.
3. The combined rate of serious procedural adverse events, including death, myocardial infarction, index limb amputation, and access site and treatment site complications requiring surgery, blood transfusion (>2 units of PRBC), or prolonged hospital stay within 30 days of the index procedure.

Secondary Effectiveness Endpoints:

1. Acute technical (lesion) success, procedural success and device success.
2. Ankle Brachial Index (ABI) and Toe Brachial Index (TBI) at 1, 6 and 12 months.
3. Target vessel revascularization (TVR) at 6 and 12 months.
4. Limb ischemia by Rutherford Becker Classification at Baseline, 1, 6, and 12 months.
5. Number of any type of index limb amputations at 6 and 12 months.
6. Absolute Claudication Distance as measured by the Exercise Tolerance Test (TASCI) assessed in 100 subjects at baseline, 1, 6, and 12 months.
7. Target lesion revascularization (TLR) at 1, 6 and 12 months.

8. The rate of primary assisted patency through follow up defined as: revascularization of non occlusive (<99%) stenosis within the stent graft or immediately above or below the treated arterial segment with less than 50% residual stenosis.
9. The rate of secondary patency through follow up defined as: revascularization of occlusion (100%) within the stent graft or immediately above or below the treated arterial segment with less than 50% residual stenosis.

Additional Secondary Endpoints:

The following additional endpoints will also be reported:

1. A combined rate of death at 30 days, or TLR, index limb amputation, and an increase in Rutherford Becker Classification by 2 classes (comparing pre to post procedural assessments) measured at 24 months.
2. Target vessel revascularization (TVR) at 24 months post procedure.
3. Limb ischemia improvement by Rutherford Becker (improvement in scale by ≥ 1) at 24 months.
4. Major Adverse Vascular Event (MAVE) by 24 months, defined as: Stent thrombosis, target limb amputation, or clinically apparent distal embolization, defined as causing end organ damage (e.g. lower extremity ulceration, tissue necrosis, or gangrene).
5. Procedure related arterial rupture, acute limb ischemia, or bleeding event requiring transfusion. Number of any type of index limb amputations at 24 month follow up. Target lesion revascularization (TLR) at 24 months post procedure.

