6.4 Withdrawal of Subjects

Each subject may voluntarily withdraw his/her participation from the study at any time. Investigators may discontinue a subject's participation in the study as deemed appropriate per safety measures and/or if the subject's medical condition contraindicates further study participation. All enrolled subjects will undergo the complete study follow up for safety evaluation.

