11.0 ENDPOINTS AND STATISTICAL ANALYSIS PLAN**11.1 Endpoints Analyses and Reporting of Results**

The study objective is to assess the safety and performance of the PQ Bypass Stent Graft System to access, deliver guidewires and implant stent grafts. The statistical methods for the primary endpoints are pre specified in this analysis plan and cannot be changed at the time of analysis.

All subjects will be followed on an intent to treat basis. The device performance will be assessed based on a per protocol analysis of the primary safety and effectiveness endpoints. An Intent to treat analysis, along with other secondary analyses, will also be completed and reported. Demographic, baseline clinical and disease characteristics, procedural results and primary, secondary and all additional endpoints will be summarized using descriptive statistics. All statistical analyses will be performed using SAS for Windows version 9.1 or higher.

As noted above, up to 65 subjects with a documented untreated, atherosclerotic lesions of the native superficial femoral artery (SFA) or the superficial femoral and proximal popliteal arteries, suitable for treatment with PQ Bypass Stent Graft may be enrolled in the study to ensure an appropriate sample size of 60 evaluable subjects post treatment.

- Safety assessment will be achieved by recording and measuring Major Complication rates/Serious Adverse Event rates associated with the PQ Bypass stent grafts. The primary safety endpoint (MAE) and MAVE will be presented using descriptive statistics at various time intervals. Using the Wilson Method, the one sided upper 95% confidence bound will be calculated and presented.
- The primary performance hypothesis will be tested by calculating the one sided 95% lower confidence limit for the rate of successful performance using the Wilson Method. If the lower limit exceeds the performance goal rate of 70% the null hypothesis will be rejected and the endpoint will be met. In addition to hypothesis testing, descriptive statistics of the primary performance endpoint will include the total number and percentage of patent PQB grafts.
- Descriptive statistics of the primary performance endpoint which includes total number of patent PQ Bypass grafts, percentage of patent PQ Bypass grafts, and the one sided 95% CI of the percentage using the Score approximation will be presented. The lower bound of the one sided 95% CI will be will be calculated and presented.

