11.6 Imputation for Missing Data

Imputations for missing data in (e.g. withdrawn subjects, loss to follow up, missing data) will not be performed. Analyses will be performed with all available data only.

12.0**ADVERSE EVENTS**

The occurrence of Adverse Events will be monitored during this study. All Adverse Events will be recorded on the Adverse Event Form at onset and at each follow up visit until resolved. To meet the objectives of this study, the following definitions will apply. (Definitions reference ISO 14155:2011 01). Potential adverse events associated with use of the SGS include, but are not limited to the following:

 • Access site hemorrhage or hematoma • Access site pain/infection • Acute vessel closure • Aneurysm or pseudoaneurysm formation • Arteriovenous (AV) fistula • Death • Device failure • Embolism • Fever/pain in absence of infection • Infection 	
 • Inflammation • Malposition • Myocardial infarction • Radiation injury • Renal insufficiency/failure due to excessive contrast load • Sepsis • Shock • Side branch occlusion • Stenosis or Occlusion • Thrombosis • Vessel dissection, perforation or wall trauma
--	--

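### The 24-month Rutherford improvement rate has no rule for re-intervention, amputation or death, so it can overstate the benefit attributable to the graft

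*Combined protocol and SAP*

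**What the plan says.** Section 5.2, Additional Secondary Endpoints, item 3 reads "Limb ischemia improvement by Rutherford Becker (improvement in scale by ≥ 1) at 24 months". The definition contains a measure, a threshold and a visit, and nothing else.

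The earlier clinical measures in the same section are also defined by measure and visit only: "Limb ischemia by Rutherford Becker Classification at Baseline, 1, 6, and 12 months" and "Ankle Brachial Index (ABI) and Toe Brachial Index (TBI) at 1, 6 and 12 months", with absolute claudication distance at baseline and the same three follow-up visits. These carry no threshold for success.

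Three other statements determine which readings reach the analysis:

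- Section 6.4: "All enrolled subjects will undergo the complete study follow up for safety evaluation".
- Section 11.1: "All subjects will be followed on an intent to treat basis".
- Section 11.6 rules out imputation and adds: "Analyses will be performed with all available data only".

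The primary effectiveness endpoint in Section 5.2 does have a re-intervention rule. It requires a patent stent on duplex ultrasound in the 12-month window "with no clinically driven re intervention within the stented segment".

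**The concern.** The stated objective is to evaluate the safety and effectiveness of the stent graft, in a single-arm study. Once a failed graft has been re-treated or bypassed, the limb's Rutherford class reflects the rescue procedure as well as the graft. With no control arm, nothing in the design exposes that difference.

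The silence works in one direction at two places. A subject whose graft occludes, who is then re-treated and is better at 24 months, enters the numerator. A subject who dies, or who has no reading after amputation, enters neither numerator nor denominator. A reader of the 24-month figure could take it as durable benefit from the device when part of it was earned by a second procedure.

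Elsewhere the plan keeps these results apart. Primary patency fails on re-intervention, and primary assisted and secondary patency are reported as separate quantities. The 12- and 24-month composites join TLR and amputation to Rutherford worsening. Rutherford improvement has no corresponding link.

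**Working it through.** **The plan's own figures.** The documents give no expected value for Rutherford improvement, so there is none to reproduce. The only sample-size figure concerns 12-month patency: 50 subjects for a 70% goal, an 85% true rate, one-sided alpha 0.05 and 80% power (Section 11.1, Table 23). An exact binomial calculation first meets those conditions at n = 49 (40 or more successes, alpha 0.0480, power 80.9%). The normal approximation gives 49.4, which rounds up to 50. The figure is sound to within one subject and does not depend on the endpoint discussed here.

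**What the default analysis does.** Setting the passages side by side:

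1. Re-treated subjects remain in follow-up (6.4, 11.1), so they have a 24-month Rutherford reading.
2. No passage removes or fails a reading taken after re-treatment, and all available data are used (11.6). The reading therefore counts.
3. A subject without a reading is not imputed (11.6) and so is not counted.

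**Size of the numerator effect.** Let N be the subjects with a 24-month reading, a the number improved and never re-treated, r the number re-treated, and s the share of those r who read as improved.

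- As-observed rate = (a + s·r)/N
- Re-intervention-free rate = a/N
- Difference = s·r/N, the re-treated fraction times s. It does not depend on a.

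Take N = 60, the evaluable number in Section 5.4, and assume that all 60 have a reading. Neither the re-treated fraction nor s is given for this study, so both are assumptions.

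| Re-treated by 24 months | s = 50% | s = 100% |
|---|---|---|
| 10% (6/60) | 0.10 × 0.5 = 5 points | 0.10 × 1.0 = 10 points |
| 20% (12/60) | 0.20 × 0.5 = 10 points | 0.20 × 1.0 = 20 points |

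The range is 5 to 20 points, and it scales in proportion if more subjects are re-treated.

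**One worked case.** Suppose 9 of 60 are re-treated. Of the other 51, 90% improve (0.90 × 51 = 45.9, taken as 46), and 8 of the 9 re-treated limbs read as improved.

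- As observed: (46 + 8)/60 = 54/60 = 90.0% (95% score interval 79.9% to 95.3%)
- Re-intervention-free: 46/60 = 76.7% (64.6% to 85.6%)
- Difference: 8/60 = 13.3 points

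**Where the 10% to 20% comes from.** Table 10 (Section 2.3) shows 14.3% (5/35) TLR/TVR at 12 months in STP 115. That rate lies inside the range and helps to set it, but it is not an estimate for this trial. STP 115 used the same graft routed through the vein as a bypass, in lesions averaging about 28 cm, against 8 to 18 cm here. It is also a 12-month rate, and the endpoint is read at 24 months.

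**Size of the denominator effect.** Not estimated. Table 10 shows 0/35 deaths and 0/35 amputations at 12 months in STP 115, which gives no basis for a figure at 24 months. Only the direction is clear: such subjects can only lower the rate if they are kept in the denominator as not improved.

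**The case against.** The strongest reply is that reading status at the visit regardless of re-treatment is a legitimate treatment-policy estimand, and it fits follow-up by intent to treat. That stands. The defect is that the plan does not declare it, and that it offers no companion figure isolating the graft. The as-observed rate should be kept.

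A second reply is that re-treatment is already visible. TLR is reported at 1, 6, 12 and 24 months, TVR at 6, 12 and 24 months, and amputations at 6, 12 and 24 months, with primary assisted and secondary patency besides. This narrows the gap without closing it: separate totals do not show how many of the improved subjects had been re-treated.

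A third reply is that no claim rests on this endpoint. It is summarised descriptively, in the lowest tier of endpoints, and the only hypothesis test is on 12-month patency. This also stands, and it limits the importance of the point.

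Several stronger readings are tempting and are not supported:

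- *That the plan counts rescue results as device success.* No passage says so. The inclusion of post-rescue readings follows from silence plus the available-data sentence, and device success is a separate item listed with acute technical and procedural success.
- *That ABI, walking distance and the 1-, 6- and 12-month Rutherford summaries have inflated success rates.* They have no success threshold, so there is no numerator to inflate. Post-re-intervention values can still shift their averages or distributions.
- *That the assumed 15% loss of patency is a re-treatment rate.* A velocity ratio of 2.5 or more fails patency without any re-intervention.
- *That any TVR should count as graft failure.* Section 19 defines TVR as treatment of another lesion. Failing on it would penalise a patent graft for disease elsewhere.

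**Conclusion.** The point holds for the 24-month Rutherford improvement rate. The plan has no rule for re-intervention, amputation or death there, and its default can make the rate overstate the benefit attributable to the graft. The direction follows from the text. The size does not: the 5 to 20 points rest on assumed re-treatment of 10% to 20% and assumed improvement in 50% to 100% of re-treated limbs, and they measure the gap between two estimands, not an error in either.

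Item 3 speaks of a scale, and the Schedule of Assessments (note 7) collects both a Clinical Category and a Clinical Improvement score at follow-up. The point is the same whichever is meant.

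The primary endpoint, its test, alpha and sample size are untouched. This is an inexpensive improvement in reporting and does not threaten the trial's main conclusion.

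**What to change.** For the 24-month endpoint, state two rates in Section 11.4:

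1. The as-observed rate, kept and labelled as regardless of re-intervention, with the number of subjects who have no reading and why.
2. The proportion improved by at least 1 at 24 months without clinically driven re-intervention of the stented segment or index lesion (including surgical bypass of it), index-limb amputation or death. Subjects with any of these events count as not improved and stay in the denominator. TVR of another lesion does not count as failure.

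Surgical bypass should be named because the TLR definition in Section 19 does not say whether it is included.

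For Rutherford class at 6 and 12 months, ABI and walking distance, give the number re-treated before each visit and add a summary excluding values taken after re-intervention. That summary describes only limbs not yet re-treated, so it should be read with the count beside it.

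The cost is SAP wording, one more table line for the 24-month endpoint and the added summaries for the earlier visits. The plan already calls for Rutherford scores, TLR, amputations and deaths, and the primary endpoint already needs re-interventions classed as clinically driven. No visit or subject is added. The restriction in Section 11.1 on changing methods covers the primary endpoints only, so it does not stand in the way. The downside is a second figure less favourable than the first. The rule should be fixed before the 24-month data are analysed, so that the choice is not made after seeing which version looks better.

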5.3 Study Duration

This study is expected to commence enrollment in the first quarter of 2016. Enrollment of all subjects is expected to be completed in the second quarter of 2016.

5.4 Number of Subjects and Sites

Up to 65 subjects may be enrolled. A total of 60 evaluable subjects with a documented untreated, atherosclerotic lesions of the native superficial femoral artery (SFA) or the superficial femoral and proximal popliteal arteries, suitable for treatment with PQ Bypass™ Stent Graft System.

5.5 Inclusion Criteria

The subject must meet all of the following criteria at the time of eligibility:

1. Age ≥ 18 years and of age of legal consent.
2. Women of child bearing potential must have a negative pregnancy test within 7 days prior to the index procedure.
3. Subject has lifestyle limiting claudication or rest pain (Rutherford Becker scale 2-4*) with a resting ABI < 0.9 . Resting TBI is utilized only if unable to reliably assess ABI. TBI must be < 0.7 . These assessments are required for the target limb, but both limbs are preferred.
4. A superficial femoral artery lesion with $> 50\%$ stenosis or occlusion which requires treatment.

5. Stenotic lesion(s) or occluded length within the same vessel (one long or multiple serial lesions) $\geq 80\text{mm}$ to $\leq 180\text{mm}$.
6. Reference vessel diameter (RVD) $\geq 5.0\text{mm}$ and $\leq 6.7\text{ mm}$, angiographically/CTA/MRA defined.
7. Patent popliteal artery 3 cm proximal to tibial plateau
8. At least 1 patent tibial artery to the foot (<50% stenosis)
9. The target lesion(s) can be successfully crossed with a guide wire and dilated.
10. Adequate aortoiliac or common femoral "inflow" is defined as <30% stenosis after either PTA or stenting of the inflow lesion. After treatment of the inflow lesion, the residual pressure gradient across the target lesion will be obtained and if the peak to peak pressure gradient is < 20mmHg, the subject will be included in the study. Subjects enrolled with aortoiliac or common femoral artery lesions resulting in poor inflow, must be treated prior to receiving the study treatment. (Same Day or earlier)
11. If a subject has bilateral obstructive SFA disease, only 1 leg may be treated with the investigational device in the study.
 - a. If the study leg is treated first, the contra lateral procedure should not be performed until at least 30 days after the index procedure (staged); and should only be performed with an approved (CE Marked) device.
 - b. If the contra lateral leg is treated with an approved (CE Marked) device prior to treatment of the study leg, treatment of the contra lateral leg should be performed at least 15 days prior to the treatment of the study leg.
12. The subject is eligible for standard surgical repair, if necessary.
13. A subject who requires a coronary intervention should have it performed at least 30 days prior or 30 days post the treatment of the target lesion.
14. Subject must provide written informed consent.
15. Subject must be willing to comply with the specified follow up evaluation schedule.

*Note – Patients with stage 2 Rutherford classification can be included when conservative physical and drug therapy have been unsuccessful and documented.

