Inclusion Criteria	
The subject must meet all of the following criteria at the time of eligibility:
 
 1. Age ≥ 18 years and of age of legal consent. 2. Women of child bearing potential must have a negative pregnancy test within 7 days prior to the index procedure. 3. Subject has lifestyle limiting claudication or rest pain (Rutherford Becker scale 2-4)* with a resting ABI < 0.9. Resting TBI is utilized only if unable to reliably assess ABI. TBI must be < 0.7. These assessments are required for the target limb, but both limbs are preferred. 4. A superficial femoral artery lesion with $>50\%$ stenosis or occlusion which requires treatment. 5. Stenotic lesion(s) or occluded length within the same vessel (one long or multiple serial lesions) $\geq 80\text{mm}$ to $\leq 180\text{mm}$. 6. Reference vessel diameter (RVD) $\geq 5.0\text{mm}$ and $\leq 6.7\text{ mm}$, angiographically/CTA/MRA defined. 7. Patent popliteal artery 3 cm proximal to tibial plateau 8. At least 1 patent tibial artery to the foot ($<50\%$ stenosis) 9. The target lesion(s) can be successfully crossed with a guide wire and dilated. 10. Adequate aortoiliac or common femoral "inflow" is defined as $<30\%$ stenosis after either PTA or stenting of the inflow lesion. After treatment of the inflow lesion, the residual pressure gradient across the target lesion will be obtained and if the peak to peak pressure gradient is $< 20\text{mmHg}$, the subject will be included in the study. Subjects enrolled with aortoiliac or common femoral artery lesions resulting in poor inflow, must be treated prior to receiving the study treatment. (Same Day or earlier) 11. If a subject has bilateral obstructive SFA disease, only 1 leg may be treated with the investigational device in the study. 
 a. If the study leg is treated first, the contra-lateral procedure should not be performed until at least 30 days after the index procedure (staged); and should only be performed with an approved (CE Marked) device. b. If the contra-lateral leg is treated with an approved (CE Marked) device prior to treatment of the study leg, treatment of the contra-lateral leg should be performed at least 15 days prior to the treatment of the study leg. 12. The subject is eligible for standard surgical repair, if necessary. 13. A subject who requires a coronary intervention should have it performed at least 30 days prior or 30 days post the treatment of the target lesion.

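### Inclusion criterion 10 takes the post-treatment pressure gradient across the SFA study lesion, although its purpose is to confirm inflow

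*Combined protocol and SAP*

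**What the plan says.** Item 10 of Section 5.5 checks inflow in two steps.

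- **Anatomic step.** Adequate aortoiliac or common femoral inflow "is defined as <30% stenosis after either PTA or stenting of the inflow lesion". Subjects whose lesions cause poor inflow "must be treated prior to receiving the study treatment", on the same day or earlier.
- **Pressure step.** After the inflow lesion has been treated, "the residual pressure gradient across the target lesion will be obtained and if the peak to peak pressure gradient is < 20mmHg", the subject is included.

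The Protocol Summary carries the same wording: "the residual pressure gradient across the target lesion will be obtained". The list opens with "The subject must meet all of the following criteria at the time of eligibility", so item 10 is a condition of entry and not advice.

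**The concern.** The two steps of item 10 refer to different lesions. The anatomic step looks at the inflow lesion. The pressure step looks at the target lesion, which everywhere else is the SFA lesion under study. A pressure drop across the SFA lesion does not show whether the aortoiliac or common femoral segment upstream is still obstructed.

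Two things are at stake:

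- In subjects with a treated inflow lesion, a site that follows the text makes no pressure check of inflow, and only the under-30% stenosis test remains.
- Sites may apply the step differently. One may measure the SFA lesion as written, while another measures the inflow lesion because that is clearly the purpose. The second departs from the text, and Section 15.0 requires the sponsor's prior approval for a knowing deviation.

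**Working it through.** The protocol states no figure to reproduce here. The check is a comparison of wording, followed by one illustration.

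**1. What the target lesion means.** There is no formal definition, but usage is consistent.

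| Place | Wording or content | Lesion meant |
|---|---|---|
| Section 5.5, item 9 | "The target lesion(s) can be successfully crossed with a guide wire and dilated" | Study (SFA) lesion |
| Section 5.5, item 13 | coronary intervention timed to at least 30 days before or "30 days post the treatment of the target lesion" | Study (SFA) lesion |
| Section 19.0, Target Lesion Revascularization | repeat intervention at the index lesion site | Study (SFA) lesion |
| Section 5.5, item 10, start of the gradient sentence | names the inflow lesion separately | Aortoiliac or common femoral lesion |

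The gradient sentence starts with one term and then moves to the other, so as written these are two different lesions.

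**2. What the step was meant to measure.** The item is about inflow, the gradient follows treatment of the inflow lesion, it is called *residual*, and a low value leads to inclusion. All four features fit the lesion just treated.

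**3. Does timing rescue the wording?** Section 6.2 confirms eligibility before the device is inserted, after the wire has crossed the lesion and the lesion has been dilated. Section 8.1 lists imaging, sheath and wire crossing only. Neither mentions the gradient.

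- *Before SFA dilatation:* item 4 requires more than 50% "stenosis or occlusion which requires treatment", while item 10 would require a small pressure drop across that same lesion. The two sit badly together.
- *After SFA dilatation:* that conflict falls away, but the gradient is still not taken across the inflow lesion.

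The wrong segment is measured in both cases.

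**4. Illustration of the first case.** Assume a brachial systolic pressure P of 120 to 160 mmHg (not given in the protocol), and that nearly all of the resting drop from aorta to ankle lies across the SFA lesion. Then drop = P × (1 − ABI).

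- ABI at which the drop is 20 mmHg: 1 − 20/120 = 0.833; 1 − 20/140 = 0.857; 1 − 20/160 = 0.875.
- Drop at ABI 0.65, the mean in the sponsor's STP 115 study (Table 6): 0.35 × 120 = 42 mmHg; 0.35 × 160 = 56 mmHg.

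Item 3 admits a resting ABI below 0.9. Under these assumptions the literal rule would pass only subjects with an ABI between about 0.83–0.88 and 0.9, and would tend to turn away the haemodynamically significant lesions the study is meant to treat. This shows direction only. STP 115 treated longer lesions (mean 28.6 cm, 96.7% chronic total occlusions), and a small resting gradient across a moderate stenosis is possible, so the rule can still be met.

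**5. Is it corrected elsewhere?** No. The Change History entry for revision B3 records that criterion 10 was clarified, but both current copies still name the target lesion.

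**The case against.** The strongest reply is that the protocol does not prove which word is wrong. The sentence might have been meant to check that the SFA lesion is still significant after inflow treatment, in which case the inequality sign would be the slip and renaming the lesion would be the wrong repair. That reading is possible in isolation but does not fit an item that defines adequate inflow, calls the gradient residual and includes the subject when it is low.

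Other points stand in part:

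- The anatomic test and the rule to treat inflow first are intact, and the operators are experienced. This limits the harm but does not make the text right.
- Item 10 does not say what happens at 20 mmHg or more, and Section 5.6 has no matching exclusion. The requirement to meet every criterion implies that the subject fails entry, but this is not spelled out.
- A site that takes the phrase to mean the lesion just treated is interpreting unclear text and may not be knowingly deviating. Nothing shows that sites have in fact differed.
- An amendment may reach few subjects. Section 5.3 expects enrolment to end in the second quarter of 2016, and Section 2.3 already reports STP 115 data as of May 2016. The Protocol Summary allows 12 months for enrolment, so this is not settled.

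**Conclusion.** The criterion is wrong as written, and the point is minor. The pressure step names the SFA study lesion where the treated inflow lesion is needed. The conclusion rests on the consistent use of the term in items 9 and 13 and in the revascularization definition, and does not depend on the ABI illustration.

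Only subjects with a treated inflow lesion are affected. The protocol gives no number for them, and any effect on 12-month patency is unknown. No statistical quantity in Section 11 changes: one-sided alpha 0.05, 80% power, performance goal 70%, 50 subjects needed, 60 evaluable planned, up to 65 enrolled.

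**What to change.** In item 10 of Section 5.5 and in the Protocol Summary, replace the reference to the target lesion in the gradient sentence with *the treated inflow (aortoiliac or common femoral) lesion*. Leave the 20 mmHg threshold, the under-30% stenosis test and the treat-first rule as they are. Apply the change only to subjects enrolled after it takes effect; those already enrolled stay under the wording in force at their enrolment. Section 11 needs no change.

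The cost is one phrase in two places, a signed amendment agreed between the Principal Investigator and the sponsor, ethics committee and (when appropriate) competent authority notification, or approval where local rules require it (Section 16.4), and a notice to sites. No subjects are added. No measurement is added either, because item 10 already calls for a gradient after inflow treatment. Where inflow was treated at an earlier session, the site notice should say when the gradient is to be taken.
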